11.3 Statistical criteria of termination of trial

Only data from subjects who have completed the entire protocol will be included in the study. This ensures that all data has been collected under the same conditions and thus remains homogeneous and comparable.

11.4 Planned Analyses

11.4.1 Datasets to be analysed, analysis populations

Only complete data sets will be included in the study. Data that contains only part of the protocol is not included in the analysis. No new subject is being sought to replace the missing data.

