7.4 Criteria for withdrawal / discontinuation of participants

If a participant withdraws from the study, the allocation lot is returned to the pot in a new envelope and a new participant is sought.

The already completed consent form is kept in the locked filing cabinet. If consent is withdrawn, the data and samples already collected must be included in the analysis for scientific and safety reasons. These will only be anonymised after the analysis (Art. 9 ClinO).

The conditions for discontinuing the trial were described in chap. 5.4. There is no disadvantage for the participants if they discontinue their participation in the study.

SUPSI

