8.5 Data Collection and Follow-up for Withdrawn Participants

If consent is withdrawn, the data and samples already collected must be included in the analysis for scientific and safety reasons. These are only anonymised after the analysis (Art. 9 ClinO).

SUPSI

There is no disadvantage for the participants if they discontinue their participation in the study and no further interventions are necessary for follow-up treatment.

If study participation was discontinued due to a reaction occurring during study participation, this will be recorded and reported to the sponsor investigator (head of the research laboratory), study director and supervisor of the study. If medical treatment is required, the report will be forwarded to the business liability insurance of Thim van der Laan AG (Basler Versicherung) to ensure the appropriate follow-up treatment.

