11.4.2 Primary Analysis

The statistical data analysis will be carried out by [name] once the data collection for the entire project has been completed.

Repeated measures analysis of variance (MANOVA)

2 factors:

Factor 1: Intervention (cold water immersion vs. hot water immersion vs. hypoxia group vs. passive control intervention)

Factor 2: Time (Baseline, 0, 24 hours, 48 hours, 72 hours)

The significance level is set at $P < 0.05$, and the statistical data analysis is carried out with SPSS 27.

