11.5 Handling of missing data and drop-outs

If a test subject does not complete the experiment, any data that has already been collected is retained, but is not further incorporated into the final data analysis.

SUPSI

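### The completers-only analysis set contradicts 7.4 and 8.5 when consent is withdrawn; for other losses it is consistent, but it can bias the randomised comparison and discards recorded data

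*Combined protocol and SAP*

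**What the plan says.** Three places in section 11 restrict the analysis to completers.

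- 11.3: "Only data from subjects who have completed the entire protocol will be included in the study". The reason given is that the data then arise under the same conditions and stay comparable.
- 11.4.1: "Only complete data sets will be included in the study. Data that contains only part of the protocol is not included in the analysis".
- 11.5, on a woman who does not finish: "any data that has already been collected is retained, but is not further incorporated into the final data analysis".

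Sections 7.4 and 8.5 give the opposite instruction for one kind of loss, in identical words: "If consent is withdrawn, the data and samples already collected must be included in the analysis for scientific and safety reasons". Both cite the Swiss clinical trials ordinance.

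On replacement, 7.4 says that after a withdrawal "the allocation lot is returned to the pot in a new envelope and a new participant is sought", while 11.4.1 says "No new subject is being sought to replace the missing data".

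The primary analysis (11.4.2) is a repeated-measures (M)ANOVA with group and five levels of time: baseline, 0, 24, 48 and 72 h. No secondary analysis is planned. The plan names no all-randomised analysis set, no method for missing data and no sensitivity analysis; intention to treat appears only in the list of abbreviations.

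**The concern.** There are two separate problems.

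The first is an instruction that cannot be carried out. When a woman withdraws consent before 72 h, one section requires her data in the analysis and another excludes them, and no order of precedence is stated. Two analysts could build different analysis sets from the same document.

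The second is the selection itself. Completion is observed after randomisation and may differ by group. Participants are not blinded (6.2.2) and may stop an application that they find unpleasant (5.4, 8.1.1). Only the bath groups have a second session (table in 9.1, step 5), and 3.7 lists symptoms particular to hypoxia. Section 8.5 itself foresees stopping for such a cause: "If study participation was discontinued due to a reaction occurring during study participation, this will be recorded". If completion depends on both group and outcome, the women compared are no longer the groups formed by lot. The comparability that 11.3 seeks comes from randomisation, and selecting completers can undo it.

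**Working it through.** **Step 1. Which rule applies to whom.**

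| Situation | 7.4 and 8.5 on data use | Section 11 | Compatible? |
|---|---|---|---|
| Consent withdrawn before 72 h | analyse what was collected | exclude | no |
| Stops or misses a visit, consent stands | silent | exclude | yes |
| Cancels an application, attends every visit | silent | excluded by 11.3; arguably kept by 11.4.1, since her data set may be complete | unclear within section 11 |

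Section 7.4 uses two triggers: leaving the study (replacement) and withdrawing consent (data use). Only the second conflicts with section 11 on data use.

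**Step 2. Replacement.** Section 7.4 seeks a new participant; 11.4.1 does not. The two fit together only if 7.4 covers withdrawals and 11.4.1 covers other missing data. The text draws no such line, and a withdrawal normally leaves a partial data set. If 7.4 on replacement is combined with section 11 on exclusion, a woman who withdraws is removed and her place refilled.

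**Step 3. Recorded data discarded.** Share discarded = values recorded before loss / values scheduled. By time points (11.4.2):

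- leaves after the immediate assessment: 2/5 = 40%
- leaves after 24 h: 3/5 = 60%
- leaves after 48 h, or misses any one follow-up visit: 4/5 = 80%

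Counted by single values, the share depends on which section is followed.

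- Table in 9.1, each listed item once and three blood markers: 15 at baseline and 13 at each of four later times, so 15 + 4 × 13 = 67. Recorded after 0, 24 and 48 h: 28, 41 and 54, or 41.8%, 61.2% and 80.6%.
- Section 5.1 (blood pressure not counted): 6 before, 13 immediately after and 11 at each of three later visits, so 6 + 13 + 3 × 11 = 52. Recorded: 19, 30 and 41, or 37%, 58% and 79%.

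The time-point fractions are the figures to use.

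**Step 4. Bias.** For groups A and B and completion C, the expected completers-only difference is

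(μA − μB) + (δA − δB), where δg = E[Y | g, C = 1] − E[Y | g].

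Each δ is zero if completion is unrelated to outcome in that group. The documents give one overall loss allowance (20%, in 11.2), nothing by group and nothing on the link with outcome, so δA − δB cannot be computed.

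A simulation shows only that the mechanism works. Its assumptions are: no true effect; 10 or 15 women per group; the worst 20% at 24 h leave one group; a random 20% or nobody leaves the other; between-visit correlation 0.5 to 0.9. The mean difference at 72 h among completers was then 0.16 to 0.30 SD instead of 0, and a two-sided 5% test rejected in about 6% to 13% of runs. None of these drop-out patterns comes from the documents.

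**Step 5. What the 20% allowance covers.** The figure in 11.2 reproduces as 33 × 1.20 = 39.6, rounded up to 40. A 20% loss from 40 leaves 40 × 0.80 = 32. Taking the effect size that gives 80% power at 33 (four groups, noncentral F), power at 32 is about 78%. The allowance therefore addresses precision. It does nothing about δA − δB.

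**Step 6. Is rewording enough?** No. A repeated-measures (M)ANOVA with five time levels needs five values per woman, so it would drop early withdrawals even if section 11 were aligned with 7.4 and 8.5. A mixed model is feasible at this size: an unstructured 5 × 5 covariance has 5 × 6 / 2 = 15 parameters, and 40 women in four groups leave 40 − 4 = 36 degrees of freedom between women.

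**The case against.** The plan states its completers rule three times and consistently. It budgets for the loss in 11.2, where drop-out and incomplete data sets are the stated reasons for the 20%. By Step 5 the cost in power is small. Follow-up lasts only 72 h, payment comes after the last visit, and women who fear water or hypoxia are excluded (7.1). Section 3.7 rates the hypoxia risk as low, and 3.3 reports no side effects in earlier studies with baths at these temperatures. Loss may be rare and unrelated to group.

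Much of this stands. It limits the likely bias and largely answers the complaint about power. It does not remove the bias risk, because an allowance in the sample size cannot correct selection, and it does not touch the contradiction on consent withdrawal.

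Four stronger readings are tempting, and the documents do not support them:

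- *Every drop-out triggers the contradiction.* On data use it covers consent withdrawal only; a woman who simply stops attending falls under section 11 alone.
- *The comparison will be biased, by a known amount.* No loss rate by group or link with outcome is given, and the simulated range rests on an assumed adverse pattern.
- *The share of discarded values is the same however values are counted.* It is not, because 5.1 and 9.1 list different time points.
- *A woman who cancels a bath but attends every visit certainly loses all five time points.* That follows from the wording of 11.3 but arguably not from 11.4.1.

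**Conclusion.** The point holds and should be fixed before analysis. For a woman who withdraws consent before 72 h, 7.4 and 8.5 cannot be followed together with 11.3, 11.4.1 and 11.5. The replacement rules in 7.4 and 11.4.1 also conflict unless they are meant for different kinds of loss, which the text does not say.

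For all other losses the matter is one of analysis choice. The completers-only rule can bias the randomised comparison if completion depends on group and outcome. The size and direction cannot be estimated from the documents, and the bias is nil if loss is unrelated to outcome. What can be stated is the data discarded per affected woman: 2, 3 or 4 of 5 scheduled time points for leaving after the immediate, 24 h or 48 h assessment, and 4 of 5 for one missed follow-up visit. How many women this will affect is unknown; the plan's own allowance of 20% would be 8 of its minimum of 40.

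**What to change.** Replace 11.3, 11.4.1 and 11.5 with a single rule: all randomised women are analysed in the group drawn, each outcome using every available scheduled measurement. This satisfies 7.4 and 8.5 and deliberately goes further, since it also covers losses without withdrawal of consent.

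- **Model.** A linear mixed model (MIXED in SPSS, the software already named) with group, time and group × time. Prespecify the covariance structure, for example unstructured, with a named simpler fallback if it does not converge, and small-sample degrees of freedom (Satterthwaite or Kenward-Roger).
- **Short ordinal scales.** For scales such as thermal comfort and sensation, prespecify an ordinal model, or state that the linear model is an approximation, as the planned (M)ANOVA already is.
- **Sensitivity analysis.** Keep the completers analysis, and define whether complete means all interventions done, all visits attended or all values recorded.
- **Replacement.** Reconcile 7.4 with 11.4.1, and state that a replaced woman's data stay in the analysis in her drawn group.

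The cost is protocol and SAP wording and slightly more analysis work, with no extra participants or visits. The price is a missing-at-random assumption and a covariance choice fixed in advance. The model reduces selection bias but does not guarantee its removal, and it recovers little for women with no measurement after the intervention.

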11.4.2 Primary Analysis

The statistical data analysis will be carried out by [name] once the data collection for the entire project has been completed.

Repeated measures analysis of variance (MANOVA)

2 factors:

Factor 1: Intervention (cold water immersion vs. hot water immersion vs. hypoxia group vs. passive control intervention)

Factor 2: Time (Baseline, 0, 24 hours, 48 hours, 72 hours)

The significance level is set at $P < 0.05$, and the statistical data analysis is carried out with SPSS 27.

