Outcome(s):	
Primary outcomes
 
Physiological measurements
 
• Jump height measurement (cm)• Maximum Voluntary Isometric thigh Contraction (kg)• Muscle swelling (mm)• Blood oxygen saturation (%)• Oxygen saturation of the muscles (%)• Heart rate (bpm)• Skin temperature (°C)• Core Body Temperature (°C)• Inflammation parameters: IL6 (pg/ml), CRP (mg/dl), creatine kinase (U/L) 
Psychological measurements
 
• Dyspnea questionnaire (mod. Borg scale)• Exhaustion questionnaire (Borg scale)• Subjective muscle soreness (VAS scale)• Thermal comfort and thermal sensation 
Secondary outcomes: none

Study design:	Randomised, controlled trial

SUPSI

Inclusion / Exclusion criteria:	
Inclusion Criteria
 
• Young, healthy women aged 18 – 35 years• No surgical interventions on the musculoskeletal system in the trunk area and lower extremities• Anticonceptives 
Exclusion criteria
 
• Current injuries of any kind affecting the trunk and/or lower extremities• Injuries to the torso and/or lower extremities that occurred less than one year ago• Injuries to the trunk and/or lower extremities that occurred more than one year ago and are still causing symptoms• Fear of cold and/or hot water intervention• Fear of hypoxia• Taking medication of any kind (even self-purchased)• Pacemakers & cardiac arrhythmias• Known circulatory problems• Positive pregnancy test• Diagnosed skeletal static deviations• Appendectomy less than 2 years ago• Raynaud's syndrome
--	--

SUPSI

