H1 Skin temperature is increased by hot water immersion compared to cold water immersion, hypoxia group and passive control group during 72 hours.

Core Body Temperature (°C)

H0 Core body temperature is not increased by hot water immersion compared to cold water immersion, hypoxia group, and passive control group during a 72-hour recovery period.

H1 Core body temperature is increased by hot water immersion compared to cold water immersion, hypoxia group and passive control group during 72 hours.

Inflammation parameters (CRP, IL6, CK)

H0 Inflammation levels are not increased by hot water immersion compared to cold water immersion, hypoxia group, and passive control group during a 72-hour recovery period.

H1 The inflammation rates are increased by hot water immersion compared to cold water immersion, hypoxia group and passive control group during 72 hours.

Subjective information on shortness of breath (mod. BORG)

H0 Subjective information on shortness of breath is not increased by hot water immersion compared to cold water immersion, hypoxia group and passive control group during a 72-hour recovery period.

H1 The subjective information on shortness of breath is increased by hot water immersion compared to cold water immersion, hypoxia group and passive control group during 72 hours.

Subjective data on general exhaustion (BORG)

H0 The subjective data on general fatigue are not increased by the hot water immersion compared to the cold water immersion, hypoxia group and passive control group during a 72-hour recovery period.

H1 The subjective data on general fatigue are increased by the hot water immersion compared to the cold water immersion, hypoxia group and passive control group during 72 hours.

Subjective muscle soreness (VAS)

H0 Subjective muscle soreness is not increased by hot water immersion compared to cold water immersion, hypoxia group, and passive control group during a 72-hour recovery period.

H1 Subjective muscle soreness is increased by hot water immersion compared to cold water immersion, hypoxia group and passive control group during 72 hours.

SUPSI

Thermal comfort and temperature perception

H0 Thermal comfort and temperature perception are not increased by hot water immersion compared to cold water immersion, hypoxia group and passive control group during a 72-hour recovery period.

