11.2 Determination of Sample Size

Based on a study with a comparable setting (Ferreira-Junior et al. 2014, Fonda et al. 2013, Hausswirth et al. 2011) and outcome, the power analysis was calculated using the G*Power App (Düsseldorf, North Rhine-Westphalia, DEU), whereby a minimum number of 33 subjects was considered necessary to ensure the statistical power (0.80) to detect a parameter difference at the 5% significance level. Taking into account a possible loss of 20% of the data sets (due to drop-out or incomplete data sets), the minimum sample size is 40 participants. The following figure shows the G-Power calculation that was used to determine the sample size.

[figure not shown]

Figure: Sample Size Calculation

SUPSI

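### CK, IL-6 and CRP get the same repeated-measures ANOVA as every other outcome, with no transformation or baseline covariate specified; if they are right-skewed, this costs power at 8-10 per arm

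*Combined protocol and SAP*

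**What the plan says.** The synopsis lists "Inflammation parameters: IL6 (pg/ml), CRP (mg/dl), creatine kinase (U/L" among the primary outcomes, and section 4.2 repeats the list. Section 11.1 states a directional hypothesis for them: "The inflammation rates are increased by hot water immersion compared to cold water immersion, hypoxia group and passive control group during 72 hours".

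Section 11.4.2 gives one method for every outcome, "Repeated measures analysis of variance (MANOVA". It has a between-subject factor for the arms, "Factor 1: Intervention (cold water immersion vs. hot water immersion vs. hypoxia group vs. passive control intervention". The within-subject factor covers the visits: "Factor 2: Time (Baseline, 0, 24 hours, 48 hours, 72 hours".

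Baseline therefore enters only as a level of Time. The plan mentions no log or other transformation, no check of normality or sphericity, no non-parametric fallback and no baseline covariate. Section 11.4.3 lists no secondary analyses. Section 11.4.1 restricts the analysis to complete data sets.

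On size, section 11.2 says that "a minimum number of 33 subjects was considered necessary", raised to 40 for a 20% loss. Section 6.1 gives N = 60.

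The sources differ on the blood-sampling times. The flow chart in 9.1 has a sample at baseline, immediately after the intervention, and at 24, 48 and 72 hours. The synopsis omits the immediate sample. The text of 5.1 and 9.2.1 omits the baseline sample.

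**The concern.** CK, IL-6 and CRP are positive concentrations or activities measured before and after muscle-damaging exercise. If exercise or treatment multiplies such a value, its spread grows with its mean. For a log-normal variable with log-SD s, SD = mean × √(exp(s²) − 1), which is 0.31, 0.53 and 0.95 times the mean at s = 0.3, 0.5 and 0.8. Doubling the mean then doubles the SD. On the untransformed scale the variance is no longer constant over the five time points, and a few high responders dominate the error term.

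With baseline as just another time level, the arm effect also has to be found in a 12-degree-of-freedom interaction (3 × 4), and the stable differences between women are not used as a covariate. With about eight women per arm there is little power to spare. What is at stake is missing a real difference on three primary outcomes. A second cost is that the scale may be chosen after the data have been seen.

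**Working it through.** **1. The plan's own figures.** The 33 cannot be confirmed, because the effect size, correlation and test family stand only in a figure that is not reproduced. It is plausible: a four-arm within-between test with f = 0.25 and correlation 0.5 needs 31 (five times) or 35 (four times). The 40 reproduces as 33 × 1.2 = 39.6; dividing instead gives 33/0.8 = 41.25, so 42. Per arm, assuming equal allocation: 33/4 = 8.25, 40/4 = 10, 60/4 = 15.

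**2. Assumptions for the power check.** The documents supply four arms, five times, the 5% level and the arm sizes. Everything else is assumed:
- log-normal values, log-SD 0.3 to 1.0
- compound symmetry on the log scale, correlation 0.7
- one arm shifted by a fixed ratio at 24, 48 and 72 h

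There were 10,000 runs per cell. The four tests were repeated-measures ANOVA (RM; arm-by-time, Greenhouse-Geisser) on the raw and log scales, and ANCOVA of the 24-72 h mean on baseline (3-df arm test) on both scales.

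**3. Power, sustained effect.**

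| n/arm | log-SD | ratio | raw RM | log RM | raw ANCOVA | log ANCOVA |
|---|---|---|---|---|---|---|
| 8 | 0.3 | 1.5 | 0.98 | 1.00 | 1.00 | 1.00 |
| 8 | 0.5 | 1.5 | 0.53 | 0.65 | 0.74 | 0.78 |
| 8 | 0.5 | 2 | 0.96 | 1.00 | 1.00 | 1.00 |
| 8 | 0.8 | 2 | 0.47 | 0.75 | 0.72 | 0.85 |
| 8 | 0.8 | 0.5 | 0.26 | 0.74 | 0.49 | 0.85 |
| 10 | 0.3 | 1.5 | 1.00 | 1.00 | 1.00 | 1.00 |
| 10 | 0.5 | 1.5 | 0.67 | 0.81 | 0.85 | 0.90 |
| 10 | 0.8 | 2 | 0.59 | 0.87 | 0.82 | 0.93 |
| 10 | 0.8 | 0.5 | 0.37 | 0.87 | 0.63 | 0.92 |
| 15 | 0.5 | 1.5 | 0.87 | 0.97 | 0.97 | 0.99 |
| 15 | 0.8 | 2 | 0.81 | 0.98 | 0.95 | 0.99 |

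Loss of raw RM against log ANCOVA at 8 and 10 per arm:
- log-SD 0.3, ratio 1.5: 2 and 0 points
- log-SD 0.5, ratio 1.5: 0.78 − 0.53 = 25 and 0.90 − 0.67 = 23 points
- log-SD 0.8, ratio 2: 38 and 34 points
- log-SD 0.8, ratio 0.5: 59 and 55 points

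Where the effect is large relative to the spread (log-SD 0.5, ratio 2, n = 8), the loss is only about 4 points.

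**4. Where the gain comes from.** At n = 8, log-SD 0.8, ratio 2, changing only the scale moves power from 0.47 to 0.75. Changing only to the baseline-adjusted mean moves it to 0.72. Both together give 0.85. The raw test also treats doubling and halving unequally (0.47 and 0.26); the log test does not (0.75 and 0.74).

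**5. How firm the numbers are.** The raw RM figures also depend on the time course assumed for all arms after exercise; the log figures do not. A separate simulation of the same layout at 10 per arm, log-SD 0.8, ratio 0.5, gave 0.23-0.36 for raw RM and 0.84-0.93 for log ANCOVA, against 0.37 and 0.92 above. The table shows orders of magnitude.

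**6. No difference between arms.** At 8 to 10 per arm, raw RM rejects in 0.020 to 0.043 of runs, lowest at the largest log-SD.

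**7. Settings that favour the raw scale.**
- Near-normal values (mean 10, SD 2, shift 2.5, n = 8): raw RM 0.99, log RM 0.91, log ANCOVA 0.99.
- Additive release: skewed baseline plus a release of mean 2, SD 0.7 in units of the baseline median, one arm lower by 1, two-arm ANCOVA, 10 per arm. Raw against log power is 0.83/0.80, 0.83/0.75 and 0.83/0.62 at baseline log-SD 0.4, 0.8 and 1.2.
- Additive release in the four-arm, five-time layout, 10 per arm, baseline log-SD 0.8: raw RM 0.88, log ANCOVA 0.69.
- Effect at 24 h only (n = 8, log-SD 0.5, ratio 2): raw RM 0.95, log RM 0.96, log ANCOVA of the 24-72 h mean 0.32.

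**The case against.** The strongest objection is that the main simulation generates log-normal data with multiplicative effects, so the log analysis is close to the true model and is bound to win. Spread, correlation and effect ratio are all assumed, and the same values serve three different markers. Step 7 shows that under additive release even the direction of the difference reverses. This objection stands. It limits the point to a conditional one, and it is why the raw-scale analysis should remain as a sensitivity analysis.

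A second objection also stands: a single averaged ANCOVA drops the Time factor and fails badly when the effect is confined to one visit. The recommended model must therefore keep arm-by-time.

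Four stronger readings are tempting, and the documents do not support them:
- A reader might infer that the plan mandates the raw scale. It names no scale; raw is the default reading of its silence.
- A reader might infer that a log analysis would secure adequate power. At log-SD 0.8 and ratio 1.5, log ANCOVA itself reaches only 0.38 at 8 per arm and 0.48 at 10.
- A reader might infer that false positives are inflated. In the settings simulated, the planned test errs towards too few.
- A reader might take 8 to 10 per arm as settled. Section 6.1 gives N = 60, and the two sections must be reconciled. At 15 per arm the loss is smaller but still present.

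**Conclusion.** The point holds as a conditional one and is a cheap improvement to the plan. The documents establish that three positive-valued primary outcomes share the generic repeated-measures ANOVA, with neither a transformation nor a baseline covariate specified. They do not establish how skewed these markers are, or whether changes multiply or add.

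If the values are right-skewed with roughly multiplicative, sustained changes, the power given up at 8 to 10 per arm runs from about nothing at log-SD 0.3 to tens of percentage points at log-SD 0.5 to 0.8, less where the effect is large relative to the spread. If responses are additive or near normal, the log scale offers no gain and can cost power. The label MANOVA would also permit a multivariate test of the time effect, which was not simulated.

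**What to change.** In 11.4.2, pre-specify the following for CK, IL-6 and CRP:
- A repeated-measures model of the natural-log post-intervention values (0, 24, 48 and 72 h), with log baseline as covariate and arm, time and arm-by-time terms.
- Ratios of geometric means with 95% confidence intervals, and raw medians shown descriptively.
- The raw-scale analysis as a sensitivity analysis.
- A stated substitution for values below the assay limit.

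Align the text of 5.1 and 9.2.1 with the flow chart in 9.1 so that the baseline blood sample is named, since the covariate depends on it. Bring the synopsis into line on the immediate sample.

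The cost is a few sentences in the plan. The downsides are that effects are expressed as ratios, that the substitution rule is a further choice, and that power is lower if the true effects are additive. This exact model was not simulated. It combines the log scale and the baseline covariate that were tested above, and it keeps the time structure that the averaged ANCOVA drops.
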